All baseline clinical and experimental data will be recorded on paper case report forms and then transferred by our research coordinator [name] into computerized data forms, entering into the secure database REDCap @ UNC. Paper case report forms will be stored in double-locked storage. All computerized records will be password protected and HIPAA compliant. Access to all records will be restricted to the project investigators unless approved by the participant and the UNC IRB. Confidentiality will be maintained by storing all information under anonymous study numbers. No individual identifying information will be included in any reports on this study.

Given the design of the Px1, data regarding tremor direction, amplitude, frequency, etc. will be obtained automatically by software that integrates with the device. This will be copied into the central spread sheet with all further data collected at pretreatment visit and with subsequent study visits.

VII. Safety Monitoring Plan

In case symptoms occur outside of business hours, the subject will be provided the telephone number of the hospital page operator and the operator will be asked to page the on-call neurologist who subsequently will contact [name] directly with information. For non-urgent issues, the subjects will be asked to call [name] office number that is listed on the consent form of which the subject will receive a copy.

The PI will monitor the study for any adverse and serious adverse events. All serious adverse events will be reported to the IRB. Should there be a serious adverse event that occurs that increases the risks to the participants, the study will be stopped and an investigation will be conducted and a findings report generated before the study is resumed. At the time of enrollment, we will ensure we have an active and accurate phone number on file to contact the subject. Thereafter, weekly phone calls will be made by the PI or a designee for the first four weeks after injection visits to ask questions including but not limited to significant weakness, difficulty breathing, difficulty swallowing, injection site reactions, or other self-reported concerns.

VIII. Potential Problems and Limitations

This is a pilot study aimed at determining the feasibility of utilizing onabotulinumtoxin A therapy to reduce the amplitude of rest tremor and improve arm function. There are two novel components to the study design that have been utilized in similar studies but not directly aimed at measuring and improving rest tremor in Parkinson's. These include the ARAT (which has been utilized for arm function pre-and post-botulinum toxin injections to the upper limb, but not to assess rest tremor) and the introduction of a new measurement device (the Px1) that will provide the objective measures of tremor amplitude, frequency, and direction of movement. Although validation of the data acquired from the Px1 will occur, more traditional methods of measuring

tremor (the MDS-UPDRS tremor subscore) will be performed during the visit intervals of the study to account for the novel applications of these assessment tools.

IX. References

5. Marjama-Lyons J & Koller W. Tremor-predominant Parkinson's disease: Approaches to treatment. *Drugs & Aging.* 2000; 16 (4): 273-278.
6. Rahimi F, et al. Effectiveness of BoNT A in Parkinson's disease upper limb tremor management. *Can J Neurol Sci.* 2013; 40: 663-669.
7. Sheffield J & Jankovic J. Botulinum toxin in the treatment of tremors, dystonia, sialorrhea and other symptoms associated with Parkinson's disease. *Expert Rev Neurotherapeutics.* 2007; 7(6):637-647.
8. Trosch RM & Pullman SL. Botulinum toxin A injections for the treatment of hand tremors. *Movement Disorders.* 1994; 9(6):601-609.

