When choosing the proper targets for injection of botulinum toxins in rest tremor, without proper planning one could easily overdose the muscles and lead to weakness which may outweigh the benefits on reduced tremor amplitude. To date, studies which have evaluated the effect of botulinum toxin on rest tremor in Parkinson's disease have used typical doses effective for dystonia, later titrating doses higher to effect. Given that statistically-significant effect is based on gross characterization of tremor amplitude into previously-existing nominal scales (namely the Unified Parkinson's Disease Rating Scale tremor subscore), it would not be surprising that titrating doses "to effect" will subject the participant to higher toxin doses that, in turn, are more likely to produce clinically-evident weakness. Subsequently, these same studies have not been able to correlate reduced tremor amplitude to any clear functional improvement save for a single, recently-published open-label study on the subject. However, functional improvement in the

studies has generally only been assessed through subjective, self-reported measures/scales and not through any objective measures.

We propose there is a lesson to learn from task-specific dystonias: usually we have to utilize much lower doses of botulinum toxin in practice to avoid weakness while still providing benefit on function of the limb as measured by their ability to perform the task. Given that rest tremor inherently is not related to nor produced by increased tone, there is reason to believe that low doses of botulinum toxin may still provide reduction of amplitude without inducing weakness. Previous studies sometimes injected only involve either a set of flexor or extensor muscles while others injected a combination of both muscles involved in creating the oscillatory movement. To help reduce chances of weakness as best possible, we propose that splitting doses of botulinum injections into a combination of both flexor and extensor muscles would be safest. What remains to be seen is whether such low doses of botulinum toxin injected into a combination to both tremor-inducing flexor and extensor muscles might also lead to improvement of tremor amplitude and/or function of the limb.

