 - a. Severity/Amplitude: As measured by the MDS-UPDRS tremor subscore.
 - b. Limb function: As measured by the Action Research Arm Test (ARAT)
2. Evaluate Px1 versus expert clinical assessment and its sensitivity to detect changes based on the MDS-UPDRS tremor subscore
3. Determine whether methodology for this pilot project can feasibly be applied to a larger subsequent study that could be adequately powered to detect a clinically-meaningful effect of onabotulinumtoxin A on medically-refractory rest tremor.

ii. **Hypotheses:**

1. (A) Onabotulinumtoxin A significantly attenuates the amplitude of medically-refractory rest tremor of the upper limb in Parkinson's patients as compared to sham injections; as measured by reduction in the MDS-UPDRS tremor subscore.
1. (B) Onabotulinumtoxin A significantly improves the limb function of Parkinson's patients with medically-refractory rest tremor of the upper limb as compared to sham injections; as measured by an increase in ARAT scores.

III. Subjects

i. **Pilot group**

- **Number – 16**
 - Due to the limitations brought on by internal funding for this pilot project and the overall cost of botulinum toxin, an even number of patients was chosen after a cost analysis was completed. It was determined that we could cover the cost of 16 participants throughout the proposed course of the study.
- **Gender** – male or female
- **Ethnicity** – all, no restrictions
- **Race** – all, no restrictions
- **Age** – 45-80

ii. **Eligibility Criteria**

Inclusion Criteria:

1. At least 45 years of age, and no more than 80 years of age.
2. Meet UK Parkinson's disease brain bank diagnostic criteria
3. Have clinical evidence of rest tremor of one or both upper extremities defined as involuntary, rhythmic oscillations about any joint within the upper extremities
4. Rest tremor amplitude must be at minimum 3 cm as determined by expert opinion by a movement disorders specialist. Confirmation of amplitude measurement will

be obtained from the Px1 prior to active participation in the study but will not be used for inclusion/exclusion in study participation.

5. Rest tremor must be historically refractory to at least 2 categories of medications typically used as anti-parkinsonian agents including levodopa formulations, dopamine agonists, amantadine, and anticholinergics.
6. **Determining Medication Refractoriness:**

AFTER patient is consented:

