- a. By history, patient reports that they received no subjective benefit from two different categories of anti-Parkinsonian medications, including: levodopa replacement, dopamine agonists, anticholinergic agents, amantadine. If subject is on therapy at present, the current therapy could count towards quantifying the medications which have failed to reduce tremor, so long as tremor amplitude meets inclusion criterion “4”. Patient will be asked whether, on average, they believe their tremor has been consistently disabling over the course of the last month.
- b. Medication refractoriness will be confirmed through observation at time of peak-dose effect of one of the reported oral agents which have failed to reduce tremor. Note that within-individual intermittency and variability of rest tremor can be influenced by anxiety, stress, cold temperature, and fatigue. In an effort to reduce this variability, we will examine subjects in a comfortable area of the clinic space, providing up to 20 minutes to allow them to relax in a temperature-neutral location, and reduce anxiety.
- c. If at peak-dose effect the subject is felt to still meet inclusion criterion “4”, they will remain a possible candidate for the study.
- d. Once the movement disorder specialist considers the subject a possible candidate, the rest tremor amplitude will be assessed using the Px1. This assessment should be completed within 10-20 minutes of the assessment by the rating movement disorder specialist

7. Participants must be able to make no changes to their anti-parkinsonian medications for 150 days (study duration). Ability and safety to do so must also be determined by the participant’s treating physician and confirmed in writing prior to participating.
8. Able to provide informed consent

Exclusion criteria:

1. History of having undergone botulinum toxin injections for any other condition previously
2. Allergy to carbidopa or levodopa.
3. Prescreening Montreal Cognitive Assessment (MoCA) score less than 22
4. Prescreening muscle weakness as determined by Medical Research Council grade less than 5/5 on direct testing in the upper limb afflicted with rest tremor.

5. Pregnancy: documentation of non-pregnancy by urine pregnancy test will be obtained from all women of child-bearing potential prior to participation
6. Infection at the proposed injection site
7. Those with a pre-existing, concomitant neuromuscular disorder
8. Compromised respiratory function

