9. History of having undergone deep brain stimulation surgery for any condition

IV. Research Plan

i. Recruitment & Consent

Subjects will be recruited from outpatients at UNCH clinics. In order to determine whether a patient meets inclusion or exclusion it will be necessary to review the patient's electronic medical record at UNC Hospitals including: clinic consultation history and physical, other clinic notes, neurological imaging including brain MRI. The information collected will be limited only to that which is necessary to contact the subjects and ask if they are interested in participating in the study.

Prospective subjects will be approached in person by one of the investigators or a designee during a regularly scheduled clinic visit at the UNCH Neurology Movement Disorders Clinic. Alternatively, some prospective participants may have already expressed verbal interest during previous clinic visits for participating in future studies. For those patients, phone calls will be initiated with a script provided to explain the study and the level of their involvement. Prospective subjects will be told basic information about the study. If the prospective subject is interested, a member of the study team will obtain written informed consent. Once consent is obtained, the study team member will go through inclusion/exclusion criteria for the study. Should the consented subject qualify for the study based on these criteria through the screening process, the subject will be scheduled for the first study visit (which may or may not be on the same day as screening).

ii. Clinical Descriptive Data

Clinical descriptive data collected from subjects will include age, gender, race, ethnicity, prior and current medications used for treatment of rest tremor in Parkinson's disease, years of reported Parkinson's symptoms, MoCA score upon enrollment, other significant current or past medical conditions, current medications, and drug allergies. Data recorded from the Px1 will include tremor frequency, amplitude, and suggested joint/muscle groups involved in creating the oscillatory movement.

Study Dates and Purpose of Visits					
Visit	1	2	3	4	5
Study Day (relative to start date)	Day 0	Day 30 (+/- 6 days)	Day 90 (+/- 6 days)	Day 120 (+/- 6 days)	Day 150 (+/- 6 days)
Purpose of Visit	Screening Consenting Baseline Assessment Randomization/Blinding	Therapeutic Assessment	Baseline Assessment	Therapeutic Assessment	Assessment

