- a. For purposes of properly identifying muscles intended for injection, a portable EMG (Myoguide system from Intronix Technology Corp., or equivalent) will be attached to an appropriate gauge EMG-guided botulinum toxin needle (Myoject by Optima, or equivalent), which in turn will be used to hear/see motor evoked potentials (MEPs). Subjects will be asked to activate the muscle while needle is inserted to ensure proper placement of the needle in the desired muscle prior to injection of study solution.

l. Obtaining measurement with the Px1

- a. Duration employed for tremor assessment: 15 seconds per assessment. We will plan on obtaining 3 different measures prior to any of the interventions (saline or botulinum toxin) per visit, essentially over the course of 30 minutes. Every measurement/assessment is inherently an average, but the plan will be to average the 3 measurements to account for some variability in tremor severity as might otherwise naturally fluctuate for the participant. To help account for the effect that any pharmacotherapy has on the tremor, aim will be to assess the tremor at the expected peak dose effect time of their antiparkinsonian medication (using known, typical pharmacodynamic data) with every visit. This will require coordination with the participant to ensure timely oral delivery, as delineated above for each visit.

V. Benefits and Risks/Minimization of Risk

Benefits

There could be direct benefits to subjects who agree to participate. During the course of the study, the investigational agent (onabotulinumtoxin A) may reduce the amplitude of the participants' rest tremor. Given the nature of neurotoxins, however, this clinical effect is expected to be transient and last for no longer than three months. There will be no travel expense reimbursement and no payment for participation.

The benefits to society: given that currently rest tremor in Parkinson's disease can be disabling and refractory to oral medication options, this pilot study looks into the feasibility of injecting affecting limbs with onabotulinumtoxin A to minimize the amplitude of tremor and return prior function to affected upper extremities. Thereafter, those individuals whose tremors might be positively affected could also contribute to the workforce for longer (as rest tremor could be highly influential in making decisions to either apply for early disability or retirement).

Risks and Minimization of Risk

The Px1

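### Exclusion 1 bars earlier botulinum toxin only when given for another condition, so as written a patient already injected for the study tremor is eligible, with no minimum interval

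*Combined protocol and SAP*

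**What the plan says.** In the combined protocol and SAP, section III.ii (Eligibility Criteria), exclusion 1 reads "History of having undergone botulinum toxin injections for any other condition previously". Exclusion 9 in the same list reads "History of having undergone deep brain stimulation surgery for any condition". The condition that brings a patient into the trial is set by inclusion 3: "Have clinical evidence of rest tremor of one or both upper extremities".

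On how long toxin acts, section V (Benefits) says "this clinical effect is expected to be transient and last for no longer than three months". On earlier use in this tremor, the background refers to "studies which have evaluated the effect of botulinum toxin on rest tremor".

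Two entry rules bear indirectly on residual toxin. Inclusion 4 requires a tremor of at least 3 cm, which must still be met at peak drug effect. Exclusion 4 removes patients with "Prescreening muscle weakness as determined by Medical Research Council grade less than 5/5 on direct testing in the upper limb afflicted with rest tremor".

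**The concern.** In a crossover of toxin against saline, earlier toxin for the same tremor is the exposure most relevant to the comparison. Yet the literal rule turns away a patient injected for an unrelated condition years ago and accepts one injected recently for the study tremor.

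Two things are at stake:

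- **Baseline.** A patient still under the effect of earlier toxin would have a lowered Visit 1 tremor score, and that effect would wear off during period 1.
- **Blinding.** Section IV.iii (Study Design) requires the patient to be unaware of the solution. Someone who knows how toxin feels in that limb has a clue that a toxin-naive patient lacks. With only two periods, recognising one identifies the other.

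Aim 3 uses the pilot data to size a later study, so extra noise or earlier responders in the sample would carry forward.

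**Working it through.** The documents give no figure to reproduce: the sample of 16 is a budget figure and no power calculation was made. The check is mainly of wording, with some arithmetic for scale.

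**1. Does any other rule close the gap?**

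| Place | What it covers | Bars earlier toxin for rest tremor? |
|---|---|---|
| Exclusion 1 | Toxin for any *other* condition | No, read literally |
| Exclusion 9 | Brain stimulation for any condition | Not about toxin, but shows the inclusive wording |
| Inclusions 5 and 6 | Failure of two drug categories (levodopa, dopamine agonists, amantadine, anticholinergics) | No |
| Inclusion 7 | Stable anti-parkinsonian drugs during the 150 days | No; says nothing about toxin before entry |
| Inclusion 4 | Tremor of at least 3 cm | No; shows that tremor remains, not that it is unsuppressed |
| Exclusion 4 | Strength below 5/5 in the tremor limb | No; catches only toxin that leaves detectable weakness |
| Section IV.ii | Past and present tremor drugs recorded | No; descriptive only |

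No rule gives a minimum time since the last injection.

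**2. When could residual effect be present?** Take three months as 90 days, and let d be the days from the last tremor injection to Visit 1. Effect can last until study Day 90 − d.

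- Visit 1 (Day 0): possible if d < 90.
- Visit 2 (Day 24 to 36): possible if d < 90 − 24 = 66, and anywhere in the window if d < 90 − 36 = 54.
- Visit 3 (Day 84 to 96): possible only if d < 90 − 84 = 6.
- Visit 4 (Day 114 or later): not possible.

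The contamination therefore falls almost wholly in period 1.

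**3. Which way does it push the comparison?** Let w be the rise in tremor score between Visits 1 and 2 that is due only to earlier toxin wearing off. Period 2 is taken as clean, and residual and study effects as additive. In the toxin-minus-sham difference in change:

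- Sequence AB (toxin first): shift of +w, against toxin.
- Sequence BA (saline first): shift of −w, in favour of toxin.

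With k_AB and k_BA affected patients, the shift in the mean is w × (k_AB − k_BA)/16. If post-injection scores are compared instead, as the last sentence for Specific Aim 1a in section VI suggests, residual effect at Visit 2 reverses these signs. They still oppose each other between sequences.

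**4. Scale, for an assumed w = 1 point:**

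- One affected patient: 1/16 = 0.0625 points (that patient is 6.25% of the sample).
- Four affected, two per sequence: (2 − 2)/16 = 0.
- Four affected, all in one sequence: 4/16 = 0.25 points.

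If each affected patient has an independent one-half chance of either sequence (an assumption; the plan does not state the allocation ratio or any balancing), the expected shift is 0 and its standard deviation is w√k/16. For k = 4 this is 2/16 = 0.125 points. The chance that all four fall in one sequence is 2 × (1/2)⁴ = 0.125.

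**The case against.** The strongest reply is that this is a loose word with little practical effect.

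- **Entry rules.** A patient whose tremor still reaches 3 cm at peak drug effect, with full strength in the limb, is unlikely to have much residual toxin. Patients are also asked whether the tremor has been disabling over the past month, although no cut-off is attached. This stands in large part. Section IV.iii does say that weakness was on average not detectable at the low doses on which its paradigm is based. But the background says earlier tremor studies went to higher doses, where the strength check would do better. The rules reduce the risk and do not remove it.
- **Rarity.** A reader might infer from the background that toxin is in common use for this tremor. It describes research studies, and says brain stimulation is the one option left for medically refractory tremor. Records are also reviewed at recruitment, so earlier toxin should come to light. This stands as to frequency. As written, though, the rule would not make such a finding disqualifying.
- **Bias.** A reader might infer that the treatment effect is systematically biased. The documents do not support that. Sequence is randomised and wearing-off has opposite signs in AB and BA, so in expectation it is mostly noise. Chance imbalance remains possible at 16 patients, because the t-tests in section VI have no period term and the plan does not say that sequences are balanced.
- **Unblinding.** A reader might infer that earlier-treated patients would know their treatment. Nothing in the documents shows this. Toxin-naive patients may also notice an effect, the tremor score comes from a blinded specialist, and the self-reported diary is not in the analysis plan. What stands is only that earlier experience could help recognition, and that no entry rule addresses it.

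**Conclusion.** The gap in the text is real: exclusion 1 as worded admits a patient already injected for the study tremor, with no minimum interval, and no other provision bars this. The sponsor may have meant any condition, but the words do not say so.

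The consequences are possible, and their size cannot be estimated because the number of such patients is unknown. The scale figures rest on an assumed 1-point shift, additive effects, 90 days for three months and equal chance of either sequence. On that footing the usual result is extra noise of the order of 0.06 to 0.13 points for one to four affected patients, and 0.25 points in the unfavourable case of four in one sequence. That does not threaten the trial. It is still worth correcting before enrolment, because the correction is so small.

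A reader might go further and ask for a rule against non-study toxin during follow-up. That is a separate question of concomitant treatment and does not follow from the wording of exclusion 1.

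**What to change.** Reword exclusion 1 to: *History of botulinum toxin injection for any condition, including tremor*. This brings it into line with exclusion 9. No change to visits or analysis is needed. For non-study toxin during follow-up, it is enough for this point that any such use is recorded.

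The cost is a one-line amendment, and a few patients previously injected for their tremor become ineligible.

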- c. Baseline muscle strength assessment of limb: using Medical Research Council (MRC) muscle testing via physical examination
- d. Baseline ARAT score obtained by occupational therapist

- e. The Px1 will be used to obtain information regarding the direction of oscillation, average amplitude, peak amplitude, and frequency of the tremor. This will only serve as objective information regarding the tremor
- f. Randomization is performed for Visit 1, and after all above measures have been obtained the subject will be injected with either sham normal saline injection using 0.9% normal saline solution (no greater than 2 mL total solution) or predetermined onabotulinum toxin doses based off of affected muscle groups. Refer to table below for information regarding predetermined dosing.
- g. Patient will complete a daily diary of symptoms for 30 days starting the day AFTER the study visit, to be collected by study personnel at the following study visit. The diary includes subjective assessments of tremor severity, tremor persistence, arm weakness, and arm dysfunction.

f. Visit 2: Day 30 (+/- 6 days per visit)

- a. Participant will be assessed when they are due for their next dose of anti-Parkinsonian medication. If they are not taking anti-Parkinsonian medication, a single dose of carbidopa/levodopa 25/100mg 1 tablet will be administered. They will only take medication when instructed. Then one hour after observing a dose of anti-Parkinsonian medication (i.e. at peak-dose effect of the medication taken):
- b. Repeat MDS-UPDRS tremor subscore obtained by movement disorder specialist
- c. Repeat muscle strength assessment of limb: using MRC muscle testing via physical examination
- d. Repeat ARAT score obtained by occupational therapist
- e. The Px1 will be used to obtain information regarding the direction of oscillation, average amplitude, peak amplitude, and frequency of the tremor to then be compared to Visit 1.
- f. Patient will complete a daily diary of symptoms for 30 days starting the day AFTER the study visit, to be collected by study personnel at the following study visit. The diary includes subjective assessments of tremor severity, tremor persistence, arm weakness, and arm dysfunction.

g. Visit 3: Day 90 (+/- 6 days)

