- a. Participant will be asked to come to clinic at the time they are due for their next dose of anti-Parkinsonian medication. If they are not taking anti-Parkinsonian medication, a single dose of carbidopa/levodopa 25/100mg 1 tablet will be administered. They will only take medication when instructed. Then at peak-dose effect of the medication taken:
- b. Repeat MDS-UPDRS tremor subscore obtained by movement disorder specialist
- c. Repeat muscle strength assessment of limb: using MRC muscle testing via physical examination
- d. Repeat ARAT score obtained by occupational therapist
- e. The Px1 will be used to obtain information regarding the direction of oscillation, average amplitude, peak amplitude, and frequency of the tremor.

- f. Based on enrollment randomization from Visit 1, and after all above measures have been obtained:
 - i. If sham injection was performed at Visit 1, then onabotulinum toxin injection is performed at Visit 3 and vice versa. The same injection paradigm used in Visit 1 will be used for Visit 3 to ensure greatest level of consistency between injections.
 - g. Patient will complete a daily diary of symptoms for 30 days starting the day AFTER the study visit, to be collected by study personnel at the following study visit. The diary includes subjective assessments of tremor severity, tremor persistence, arm weakness, and arm dysfunction.
- h. **Visit 4: Day 120 (+/- 6 days per visit)**
 - a. Participant will be asked to come to clinic at the time they are due for their next dose of anti-Parkinsonian medication. If they are not taking anti-Parkinsonian medication, a single dose of carbidopa/levodopa 25/100mg 1 tablet will be administered. They will only take medication when instructed. Then at peak-dose effect of the medication taken:
 - b. Repeat MDS-UPDRS tremor subscore obtained by movement disorder specialist
 - c. Repeat muscle strength assessment of limb: using MRC muscle testing via physical examination
 - d. Repeat ARAT score obtained by occupational therapist
 - e. The Px1 will be used to obtain information regarding the direction of oscillation, average amplitude, peak amplitude, and frequency of the tremor to then be compared to Visit 3.
 - f. Patient will complete a daily diary of symptoms for 30 days starting the day AFTER the study visit, to be collected by study personnel at the following study visit. The diary includes subjective assessments of tremor severity, tremor persistence, arm weakness, and arm dysfunction.

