No power calculation can be performed. This is a pilot feasibility study to determine if onabotulinumtoxin A can be utilized to reduce resting tremor amplitude and improve arm function.

Data Analysis (Performed by [name], PhD)

Note that all statistical analysis, and as such any missing data/values/dropouts, will be performed assuming an intention-to-treat principle. All statistical estimates will be tabulated along with corresponding confidence intervals (CIs). All hypothesis tests that are observed to be not statistically significant will be reported as being inconclusive. Lastly, all data acquired for Visit 5 will be utilized for review of safety. This is to ensure that the expected washout effect is occurring and that there is expected normalization of values trending towards or back to previous baseline values. For this reason, there is an absence of any testing with the Px1 on Visit 5 (since data will not be utilized to compare to previous visits for purposes of statistical analysis).

Specific Aim 1a. The change in tremor severity effected by onabotulinumtoxin A will be compared to the change effected by sham saline. Tremor severity will be measured via the MDS-UPDRS tremor subscore. A Student's t-test will be utilized to compare postintervention measures within subjects.

Specific Aim 1b. The change in limb function as measured by the ARAT created by onabotulinumtoxin A will be compared to the change created by sham saline. A Student's t-test analysis will be used to compare change in ARAT scores within subjects.

Specific Aim 2. The strength of the correlation between MDS-UPDRS tremor subscore and tremor characteristics as assessed by the Px1 will be obtained. Will then evaluate the strength of the correlation between the change in MDS-UPDRS score and change in the ARAT score. This latter correlation will then be compared to the correlation between the change in tremor characteristics as assessed by the Px1 and the change in the ARAT score.

Specific Aim 3. Pilot data will be reviewed and trends analyzed. Subsequent power analysis will be performed to determine size of study population that is necessary to adequately measure statistically significant effect. Data regarding dropout rates will also be reviewed to determine if study methodology needs to be adjusted for a larger study population.

Interpretation of Results

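### Visit 4 is timed from study start rather than from the second injection, so it may fall 18 to 42 days after that injection, against 24 to 36 days for Visit 2 after the first

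*Combined protocol and SAP*

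**What the plan says.** In the combined protocol and SAP, the visit table in section IV.ii labels its day row "Study Day (relative to start date" and gives Visits 2 to 5 a tolerance of 6 days either way. The visit descriptions in section IV.iii repeat these days:

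- Visit 1 is Day 0, with no window. "Randomization is performed for Visit 1, and after all above measures have been obtained the subject will be injected" with saline or toxin.
- "Visit 2: Day 30 (+/- 6 days per visit" is the outcome visit for period 1.
- "Visit 3: Day 90 (+/- 6 days" is the crossover visit: "If sham injection was performed at Visit 1, then onabotulinum toxin injection is performed at Visit 3 and vice versa".
- "Visit 4: Day 120 (+/- 6 days per visit" is the outcome visit for period 2. Its Px1 readings cover direction, amplitude and "frequency of the tremor to then be compared to Visit 3".

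No passage times Visit 4 from the date on which the second injection was actually given. The words 'per visit' in the Visit 2 and Visit 4 headings give each visit its own tolerance but name no other starting point.

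For Specific Aim 1a, section VI states: "A Student's t-test will be utilized to compare postintervention measures within subjects". Aim 1b uses the same test on ARAT changes. Neither describes a term for period, sequence or time since injection. The Benefits text in section V expects the clinical effect to be temporary and to last three months at most.

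**The concern.** In a crossover, the two post-injection assessments should be taken at comparable times after their own injections. Here the first injection date is fixed at Day 0, so only Visit 2 can move. In period 2 both the injection and the outcome visit can move, and nothing ties one to the other, so the two tolerances add up.

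This matters because the plan expects the toxin effect to wear off. If the effect changes over the weeks in question, spread in days since injection becomes spread in the outcome. The planned t-test has no means of removing it, so it enters the paired differences of 16 people directly. It could also carry into the power analysis for a larger study that Aim 3 intends to base on these data. Elsewhere the protocol works to limit timing noise, with assessment at peak medication effect at every visit and three averaged Px1 readings. A looser post-injection window in one period works against that.

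**Working it through.** The plan states no injection-to-assessment window, so there is no figure of its own to reproduce. The check is interval arithmetic on the visit windows.

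**Inputs** (section IV.ii table and section IV.iii): injection 1 on Day 0; Visit 2 on Day 30 +/- 6, i.e. 24 to 36; injection 2 at Visit 3 on Day 90 +/- 6, i.e. 84 to 96; Visit 4 on Day 120 +/- 6, i.e. 114 to 126. Day 0 is taken as the day of the first injection. Section IV.i allows screening to fall on a different day from the first study visit, although the table puts screening at Visit 1.

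**Step 1: permitted intervals.**
- Period 1: 24 - 0 = 24 to 36 - 0 = 36 days; 12 days wide.
- Period 2: earliest 114 - 96 = 18, latest 126 - 84 = 42 days; 24 days wide.
- Nominal: 30 - 0 = 30 and 120 - 90 = 30 days, identical.

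**Step 2: largest gap between one participant's two elapsed times.**
- As written: 42 - 24 = 18 days, or 36 - 18 = 18 the other way.
- With Visit 4 at 30 +/- 6 days from the actual second injection: 36 - 24 = 12 days.

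**Step 3: typical spread.** Assume each visit falls uniformly in its window, independently of the others. The documents give no distribution of visit dates.
- Visit 2: SD = 12/√12 = 3.46 days (variance 12).
- Visit 4 less Visit 3: variance 12 + 12 = 24, SD = 4.90 days.
- Share of Visit 4 assessments outside 24 to 36 days: the difference of the two deviations is triangular on -12 to +12, so P(more than 6 days off) = (6/12)² = 0.25, or 0.25 × 16 = 4 participants.
- In whole days (13 × 13 = 169 combinations): 2 × (6+5+4+3+2+1) = 42 lie outside, 42/169 = 24.9%; the SDs are 3.7 and 5.3. The difference from 3.5 and 4.9 is only whole days against a continuous scale.

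**Step 4: link to the outcome.** If the toxin effect changes by b score points per day near day 30, timing contributes about b² × 12 to the variance when toxin is read at Visit 2 and b² × 24 when it is read at Visit 4. The documents give no b for the MDS-UPDRS tremor subscore or the ARAT, so this cannot be put in score units.

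**The case against.** The strongest reply is that the consequence is small and not directional, and much of it stands.

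- **No shift in mean timing.** The nominal interval is 30 days in both periods and order is randomised. The wider window applies to toxin in one sequence and to saline in the other. A reader might infer that the compared periods are unequal in a way that favours one treatment. The documents do not support that: only the permitted spread differs.
- **No sequence dependence shown.** A reader might also infer that the toxin effect would depend on the order given. With equal means and symmetric windows, that needs a response curve that bends materially between about 18 and 42 days. The documents give no onset, peak or plateau. A flat or straight-line response over that range would leave the average effect unchanged.
- **The extremes are rare and the misses short.** Under the Step 3 whole-day assumption, exactly 18 or 42 days occurs in 2 of 169 combinations (1.2%). Assessments outside 24 to 36 days miss by 56/21 = 2.7 days on average. If allocation is equal (the ratio is not stated), about 8 people get toxin second, and 0.25 × 8 = 2 of them would be read outside the Visit 2 range.
- **Other procedures discourage short intervals.** The diary begun after Visit 3 runs 30 days and is collected at the next visit, and section VII has weekly calls for four weeks after injection visits. A Visit 4 on day 18 would cut across both, so 25% is a figure under an assumption, not a forecast. These procedures set no window, however, and they support a 30-day interval from the injection itself.

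What does not stand is the expectation that staff will schedule Visit 4 from the Visit 3 date anyway. The table states a different rule.

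**Conclusion.** The point holds as a scheduling weakness at Visit 4. The text as written permits 18 to 42 days from second injection to outcome, against 24 to 36 days after the first. This follows from the stated windows and needs no assumption beyond Day 0 being the first injection day. Under uniform, independent visit dates, about a quarter of Visit 4 assessments fall outside the Visit 2 range, and the SD of days since injection is 4.9 against 3.5. The harm is avoidable, unmodelled variability in a small paired comparison. Its size in MDS-UPDRS or ARAT units is unknown, and neither bias nor order dependence is shown. It is worth correcting because the remedy is specific and cheap, not because it threatens the pilot's conclusions.

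Visit 5 is outside the point. Section VI reserves its data for safety and washout review, so its timing affects no compared outcome.

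**What to change.** Define Visit 4 as 30 +/- 6 days from the actual date of the Visit 3 injection, in both the section IV.ii table and the Visit 4 heading in section IV.iii. Record days since the most recent injection with every outcome. Both therapeutic assessments then share a 24 to 36 day window, and the largest within-participant timing gap falls from 18 to 12 days.

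Leave the Visit 5 anchor unchanged. Counting it as 60 +/- 6 days from the second injection would allow 96 + 66 = Day 162, against Day 156 now. That would move follow-up further past the 150 days of stable medication in inclusion criterion 7.

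The cost is a short wording change, with no added visits or participants. Visit 4 could then fall as early as 84 + 24 = Day 108 or as late as 96 + 36 = Day 132, outside its present Day 114 to 126. With Visit 5 kept at Day 144 to 156, the shortest gap between Visits 4 and 5 drops from 144 - 126 = 18 to 144 - 132 = 12 days. The 30-day diary begun after Visit 4 could then be collected incomplete somewhat more often than the present windows already allow.
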